2.3 Exploratory Objective and Endpoints

2.3.1 Exploratory Objective

The exploratory objective of this study is to further evaluate the efficacy, PK / pharmacodynamics (PD), and quality of life (QoL) associated with the use of CSL312 in subjects with HAE.

2.3.2 Exploratory Endpoints

Exploratory endpoints include the following:

[figure not shown]
1. The time to first attack after Day 1 and after Day 15.
2. CSL312 concentrations at scheduled time points.
3. FXII concentration and FXIIa-mediated kallikrein activity at scheduled time points.
4. Subject reported outcome measures:
 - Angioedema Quality of Life (AE-QoL)
 - EuroQoL-Group 5-Dimension 5-Level (EQ-5D-5L)
 - Work Productivity and Activity Impairment: General Health (WPAI:GH).
5. Investigator's Global Assessment of Response to Therapy (IGART).

3 Study Design and Oversight

3.1 Overall Design

This is a multicenter, double-blind, randomized, placebo-controlled, parallel-arm, phase 3 study to investigate the efficacy and safety of a single dose of SC CSL312 administered once monthly as prophylaxis to prevent HAE attacks in adolescent (12 to 17 years, inclusive) and adult subjects with HAE. This study will be conducted globally. As shown in [Figure 2](#), the study consists of a Screening Period (up to 1 month), a Run-in Period (up to 2 months), 1 Treatment Period (6 months), and either a 2-month Follow-up Period (ie, 3 months after last investigational product administration) or entry into the open-label Phase 3b Study [CSL312_3002](#).

Figure 2 **Study Overview**

Abbreviations: HAE = hereditary angioedema; OLE = open-label phase 3b Study CSL312_3002; q1M = once a month; SC = subcutaneous.

3.1.1 Screening

Following informed consent, subjects will undergo a Screening Period of up to 1 month to determine eligibility for enrollment into the study. Screened subjects who meet all the inclusion criteria and none of the exclusion criteria will enter the Run-in Period. If a subject does not meet the criteria for entering the Run-in period within 30 days, the subject may be rescreened with confirmation from the Sponsor. Rescreening is allowed once.

3.1.2 Run-In Period

After Screening, eligible subjects will enter the Run-in Period lasting at least 1 month and up to 2 months to confirm their underlying disease status and to assess their eligibility for participation in the Treatment Period. The first day of the Run-in Period may occur on the same day as Screening.

Subjects must complete at least 1 month of the Run-in Period. Additionally, subjects must experience at least 2 HAE attacks during the Run-In period to be eligible to enter the Treatment Period. Subjects who experience at least 2 attacks during the required first month of the Run-in Period may enter the Treatment period. Subjects who do not experience an HAE attack during the first month of the Run-in Period will remain in the Run-in Period for up to an additional month during which time they would be required to experience at least 2 attacks to be eligible to enter the Treatment Period and randomization (Section 4.1.3).

Subjects are not permitted to use routine prophylaxis to prevent HAE attacks during the Run-in Period ([Section 7.3](#)); however, subjects may use on-demand HAE therapy to treat HAE attacks if that medication has previously been shown to be effective ([Section 7.2](#)).

Subjects who do not meet the minimum HAE attack rate during the Run-in Period or are otherwise determined to be ineligible due to Screening assessments, will be considered Run-in failures and will not be allowed to be rescreened for participation in the study.

3.1.3 Treatment Period

Subjects meeting the eligibility criteria ([Section 4.1.3](#)) will enter the Treatment Period after the Run-in Period. If a subject is unable to enter the Treatment Period by Day 60, then CSL Behring (CSL) approval is required for the subject to enter the Treatment Period.

Eligible subjects will be randomized 3:2 to either the CSL312 Active Arm or the Placebo Arm. The duration of the Treatment Period is 6 months. Randomization will take age (≤ 17 years, > 17 years) and, for adults, baseline attack rate observed during the Run-in Period (1 to < 3 attacks / month, and ≥ 3 attacks / month) into account.

3.1.4 Follow-Up Period / Open-label Phase 3b Study Entry

Subjects who successfully complete the current study (CSL312_3001) may have the option to roll over into an open-label phase 3b Study CSL312_3002. Subjects who choose not to participate in Study CSL312_3002 are required to complete the Follow-up Visit (Day 242, which is approximately 3 months after the last dose of investigational product). For subjects who choose to participate in Study CSL312_3002, assessments collected on Day 182 will be used to fulfill applicable assessments for Day 1 of Study CSL312_3002.

Details of open-label phase 3b Study CSL312_3002 are described in a separate protocol.

3.2 Dose and Dosing Regimen

The investigational products in this study are 200 mg CSL312 and placebo.

Subjects randomized to the Active Arm will receive CSL312 SC once a month for 6 months. The first dose of CSL312 will be a 400 mg loading dose administered subcutaneously on the same day as 2 separate injections at the study site (ie, Month 1). Subsequent doses of CSL312 will be 200 mg administered SC once monthly for 5 consecutive months (ie, Months 2 through 6).

Subjects randomized to the Placebo Arm will receive volume-matched placebo once monthly for 6 months. The first dose of placebo in the Placebo Arm will be volume-matched placebo administered SC as 2 separate injections (ie, Month 1). Subjects will then receive volume-matched placebo SC once a month for 5 consecutive months (ie, Months 2 through 6).

3.3 Scientific Rationale

3.3.1 Study Design Rationale

This phase 3, multicenter, double-blind, randomized, placebo-controlled, parallel-arm study will investigate the efficacy and safety of once monthly SC dosing regimen of CSL312 for the prevention of HAE attacks in adolescent (ie, 12 to 17 years of age inclusive) and adult subjects with C1-INH HAE type 1 and type 2.

The study will include a Screening Period (up to 1 month) to assess subject eligibility, a Run-in Period (up to 2 months) for confirmation of disease activity and determination of subjects' baseline HAE attack rate, 1 Treatment Period (6 months) for confirmation of the safety and efficacy of the 200 mg CSL312 dose, and a 2-month Follow-up Period (3 months after the last administration of investigational product).

3.3.2 Dose Rationale

The proposed dose of 200 mg was selected based on the efficacy and safety observed in TP1 of Study CSL312_2001, CSL312 PK, inhibition of FXIIa-mediated kallikrein activity, and exposure-response (E-R) modeling.

The 200 mg dose administered once every 28 days (\pm 3 days) was highly effective across various efficacy endpoints and had a favorable safety profile. In addition, the 200 mg dose resulted in \sim 50% inhibition of FXIIa-mediated kallikrein activity.

To support phase 3 dose selection, an E-R model was used to simulate HAE attack rates over a wide range of CSL312 concentrations that would be expected after different dosing regimens. Based on the E-R model, the estimated daily average concentrations to achieve 50, 75, and 90% relative attack risk reduction in the baseline attack rate were 1.4, 3.3, and 7.8 μ g/mL, respectively. The median predicted minimum daily average CSL312 concentrations at steady-state following 200 mg SC once a month regimen corresponds to the 90% relative attack risk reduction in baseline attack rate in 73% of patients.

Additionally, the E-R model showed a cumulative effect of CSL312 concentration is evidenced in the reduction in the expected number of HAE attacks per month. The 200 mg SC once a month regimen is predicted to reduce the mean attack rate by approximately 91% compared to placebo. Increasing the dose beyond 200 mg is not predicted to result in significant further reductions in HAE attacks.

Finally, the exposures at the 200 mg SC dose administered monthly are not expected to cause aPTT prolongation in the majority of subjects in the phase 3 study.

Based on all the factors taken into consideration in selecting a dose for advancing the CSL312 clinical program, the 200 mg of CSL312 SC administered once monthly is expected to achieve clinically meaningful treatment effect and optimal benefit/risk ratio in subjects with C1-INH HAE type 1 and type 2.

3.4 Planned Study Duration

The duration of the study for an individual subject is expected to be approximately 7 to 11 months. This estimation is based on:

- A Screening Period of up to 1 month.
- A Run-in Period of 1 to 2 months (Run-in can occur on the same day as Screening).
- A Treatment Period of 6 months.
- A Follow-up Period of 2 months (ie, 3 months after the last administration of investigational product).

The overall study duration (ie, first subject's Screening Visit to last subject's End of Study Visit) will be approximately 19 months.

3.5 Planned Number of Subjects

This study will randomize approximately 60 subjects with C1-INH HAE type 1 or type 2.

3.6 Definition of Start of the Clinical Study

The start of the clinical study is defined as the date of the first act of recruitment of a potential subject at a study site.

3.7 Definition of End of the Clinical Study

The end of the clinical study (ie, completion of the study at all participating study sites) is defined as either the date of the last visit of the last subject at their Follow-up Visit (ie, Day 242) or the date of the last subject's enrollment into the open-label phase 3b Study CSL312_3002.

3.8 Study Oversight

3.8.1 Independent Data Monitoring Committee

An independent data monitoring committee (IDMC) will be established to monitor the safety and efficacy data generated during the study. The IDMC will consist of an independent statistician and clinical specialists in the fields of HAE management, who also have experience in clinical trials. The IDMC will review accumulating data from the ongoing study. Based on these reviews, the IDMC will advise on the further conduct of the study. No success or futility thresholds will be set for the IDMC reviews; CSL will not stop the study unless a major safety issue has been identified. The composition, activities, and responsibilities of the IDMC will be described separately in the IDMC charter.

3.9 Halting Criteria

3.9.1 Study Halting Criteria

Individual Subject

If a subject meets any of the following criteria during participation in the study, then further administration of CSL312 to that subject will be halted (i.e., temporarily paused) until an assessment of that subject's safety is completed: Prolonged symptoms of severe hypersensitivity considered by the investigator and/or CSL to be related with CSL312 administration; a confirmed diagnosis of TEE or a clinically significant abnormal bleeding event, irrespective of CSL312 causality; or any event or laboratory abnormality that is considered by the investigator and/or CSL to pose an unacceptable risk to the subject in the study.

Study Level

If any of the following criteria are met, then all further administration of investigational product and further enrolment of new subjects will be halted (ie, temporarily paused) until an

assessment of the overall safety of continuing the study is completed: 1 subject develops an SAE that results in death and is considered by the investigator, IDMC and / or CSL to be related to the administration of CSL312; or 1 subject develops any event that is deemed to pose an unacceptable risk to other subjects in the study, and these events are considered by the investigator, IDMC and / or CSLB to be related to the administration of CSL312.

If any study halting criteria are met and the study is halted per IDMC recommendation, the CSL Global Safety Committees will conduct a safety assessment to establish if the study should be resumed or if the temporary halt should continue. The study can be resumed on the recommendation of CSL's Global Safety Committees, in agreement with the IDMC, if the safety assessment concludes that no further study modifications, protocol amendments, or risk mitigation measures are necessary and it is safe to resume the study. Regulators (on a conditional basis) and the Independent Ethics Committee (IEC) will be notified of the temporary halt and subsequent resumption of the study. A substantial protocol amendment will be submitted to the Regulators and the IEC for approval if the safety assessment concludes that modifications to the protocol (including addition of new risk mitigation measures) are required to resume the study. Ad-hoc unblinding procedures may be initiated as per CSL standard operating procedures for further safety assessment, if needed. If the risk assessment concluded that continued dosing poses an unacceptable risk to subjects and no further risk mitigation steps can be applied, the CSL Global Safety Committees will be involved in recommending a study stop. Regulators and the IEC will be notified of a study stop.

4 Selection and Withdrawal of Subjects

4.1 Eligibility Criteria

The study population will be selected on the basis of the inclusion and exclusion criteria described in the sections below. Each subject should meet all of the inclusion criteria and none of the exclusion criteria for this study. Subject eligibility should be reviewed and documented by an appropriately medically qualified member of the investigator's study team before subjects are included in the study.

4.1.1 Inclusion Criteria for Entry into the Run-in Period

To be enrolled into the Run-in Period of this study, subjects must meet all of the following inclusion criteria:

1. Capable of providing written informed consent and willing and able to adhere to all protocol requirements and/or the subject's parent(s) or legally acceptable representative(s) capable of providing written informed consent/assent as appropriate.
2. Male or female.
3. Aged \geq 12 years at the time of providing written informed consent or assent for minors.
4. Diagnosed with clinically confirmed C1-INH HAE:
 - a. Documented clinical history consistent with HAE (subcutaneous or mucosal, nonpruritic swelling episodes without accompanying urticaria), and
 - b. C1-INH antigen and/or functional activity \leq 50% of normal as documented in the subject's medical record, and
 - c. C4 antigen concentration below the lower limit of the reference range as documented in the subject's medical record.
5. Experienced \geq 3 HAE attacks during the 3 months before Screening, as documented in the subject's medical record.

Note: For subjects taking any prophylactic HAE therapy during the 3 months before Screening, \geq 3 HAE attacks may be documented over 3 consecutive months before commencing the prophylactic therapy.

4.1.2 Exclusion Criteria for Entry into the Run-in and Treatment Periods

Subjects must not be enrolled into the study if they meet any of the following exclusion criteria:

1. Concomitant diagnosis of another form of angioedema, such as idiopathic or acquired angioedema, recurrent angioedema associated with urticarial or HAE type 3.
2. Any preplanned major surgeries or procedures during the clinical study.

3. For adult subjects: Use of C1-INH products, androgens, antifibrinolytics or other small molecule medications for routine prophylaxis against HAE attacks within 2 weeks prior to the Run-in Period.
4. For adolescent subjects 12 to 17 years of age, inclusive: Use of long-term prophylactic therapy for HAE before Screening.
5. Use of monoclonal antibodies such as lanadelumab (Takhzyro[®]) within 3 months prior to the Run-in Period.
6. Use of estrogen-containing medications with systemic absorption (eg, oral contraceptive or hormonal replacement therapy), angiotensin-converting enzyme (ACE) inhibitor within 4 weeks prior to the Run-in Period, or currently receiving a therapy not permitted during the study as defined in [Section 7.3](#).
7. Participation in another interventional clinical study during the 30 days before Screening or within 5 half-lives of the final dose of the investigational product administered during the previous interventional study, whichever is longer.
8. Known or suspected hypersensitivity to monoclonal antibody therapy or hypersensitivity to the investigational product or to any excipients of the investigational product.
9. Subject has any condition that in the judgement of the investigator or CSL, may compromise their safety or compliance, impede successful conduct of the study, interfere with interpretation of the results or would otherwise render the subject unsuitable for participation in the study, eg, clinically significant bleeding due to coagulopathy, thrombotic disorder, significant illnesses or major comorbidities.
10. Previously administered CSL312 in another interventional clinical study.
11. Intention to become pregnant or to father a child at any time during the study.
12. Female of childbearing potential or male subjects who are fertile and sexually active either not using or not willing to use an acceptable method of contraception to avoid pregnancy during the study and for 30 days after receipt of the last dose of investigational product. Acceptable methods of contraception are defined in [Section 7.4](#).

Note: All female subjects are assumed to be of childbearing potential except:

- Subjects aged > 60 years.

- Subjects aged 45 to 60 years (inclusive) with amenorrhea for \geq 1 year with documented evidence of follicle-stimulating hormone level $>$ 30 IU/L. If the follicle-stimulating hormone value is not available before randomization, a urine pregnancy test is required.
- Subjects who are surgically sterile for at least 3 months before providing informed consent.

Note: All male subjects are assumed fertile except subjects who are surgically sterile for at least 3 months before providing informed consent

13. Pregnant, breastfeeding, or not willing to cease breastfeeding.
14. Involved in the planning and / or conduct of the study (applies to CSL staff, staff at the study site, and third-party vendors).

4.1.3 Criteria for Entry into the Treatment Period

Subjects will be eligible to exit the Run-in Period and enter the Treatment Period if they meet all the following criteria:

1. Participated in the Run-in Period for at least 1 month.
2. Experienced at least an average of 1 HAE attack per month during the Run-in Period (eg, experienced a total of at least 2 HAE attacks).
3. Does not have laboratory clinical abnormalities assessed as clinically significant by the investigator in results of hematology, chemistry, or urinalysis assessments.
4. C1-INH functional activity and antigen, and C4 antigen concentration levels have been verified prior to randomization.

Note: Subjects with \geq 2 times the upper limit of normal for aspartate aminotransferase and / or alanine aminotransferase may be eligible for participation if there is an explanation for this laboratory result and if the results are not clinically significant.

4.2 Screen Failures

Screen failures are defined as individuals who consent to participate in the clinical study but who do not meet the eligibility criteria for participation in the study (see [Section 4.1](#)). A minimal set of information including demography, eligibility criteria, and screen failure details should be recorded for all individuals considered screen failures.

If a potential subject is not eligible for entry into the Run-in Period within 30 days after providing informed consent, then the subject may reconsent and may be screened again (for a maximum of 2 Screening Periods per subject) after consultation with CSL. In the event that a potential subject is screened twice, all Screening assessments must be repeated during the second Screening Period.

4.2.1 Run-in Period Failures

Run-in period failures are defined as subjects who are not eligible to enter the Treatment Period. Subjects who enter the Run-in Period but are not eligible to enter the Treatment Period will be considered Run-in failures and cannot be rescreened. The primary reason for Run-in failure must be documented for subjects not eligible to enter the Treatment Period.

4.3 Discontinuation of Study Treatment and Subject Withdrawal

4.3.1 Discontinuation of Study Treatment

Subjects may discontinue study treatment with CSL312 at any time at their own request, or at the discretion of the investigator or CSL for safety, behavioral, or administrative reasons.

Subjects who discontinue treatment with CSL312 will be encouraged to remain in the study until Day 182 in order to collect study assessments. Refer to Section 4.3.2 for details on handling subject withdrawals.

4.3.2 Subject Withdrawal

Subjects may withdraw from the study at any time at their own request, or at the discretion of the investigator or CSL for safety, behavioral, or administrative reasons (eg, because of an AE, protocol deviation, loss to follow-up, subject noncompliance, study termination). If discontinuation occurs before Day 182, subjects who discontinue investigational product will be encouraged to remain in the study until Day 182 in order to collect study assessments and complete the End of Treatment Period Visit. If the subject withdraws from the study, and also withdraws consent for disclosure of future information, CSL may retain and continue to use any data and samples collected before withdrawal of consent.

The investigator should record in the electronic case report form (eCRF) and in the subject's medical records the reason and date of subject withdrawal.

In accordance with the International Council for Harmonisation of Technical Requirements for Pharmaceuticals for Human Use (ICH) principles of Good Clinical Practice (GCP), the investigator always has the option to advise a subject to withdraw from the study if the subject's safety or wellbeing is compromised by his or her further participation in the study. Concern for the interests of the subject must always prevail over the interests of the study.

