10.3.2 Efficacy Analyses

10.3.2.1 Primary Estimand

The primary interest is to assess the treatment effect of CSL312 during treatment from Day 1 through Day 182 while subjects are allowed to treat HAE attacks with on-demand medications, administered according to [Section 5.2.1.1](#).

The primary estimand in line with the primary interest of the study follows the treatment policy strategy and is described as follows:

- Population: the target patient population defined by eligibility criteria and who were randomized (ITT).
- Variable: time-normalized number of HAE attacks during treatment from Day 1 through Day 182.
- Intercurrent events: The occurrence of an intercurrent event is irrelevant. All observed values will be used regardless of occurrence of any of the following intercurrent events:
 - administration of on-demand medication in addition to prophylactic treatment with CSL312.

- non-compliance to treatment.
- early discontinuation.
- Population-level summary: median time-normalized number of HAE attacks per month during treatment from Day 1 through Day 182 by treatment.

Subjects will be followed after failure to administer or to continue CSL312 treatment until their completion of the study, ie, Visit Day 182 or Early Termination Visit (whichever occurs first).

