13.4 Protocol Deviations

All instances where the requirements of the clinical study protocol were not complied with will be tracked. Corresponding subjects may be withdrawn from the study at the discretion of the investigator and / or CSL. Clinical study protocol deviations arise when either subjects who have been entered in the study and / or the study sites deviate from the IEC / IRB-approved study protocol.

If a major protocol deviation (ie, a deviation that could have a significant effect on the subject's safety, rights, or welfare and / or on the integrity of the study data) occurs, the investigator must notify CSL and the appropriate IRB / IEC as soon as possible or as per local requirements.

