10.1.1 Primary Estimand

The primary interest is to assess the treatment effect of CSL312 during treatment from Day 1 through Day 182 while subjects are allowed to treat HAE attacks with on-demand medications.

The primary estimand in line with the primary interest of the study follows the treatment policy strategy and is described as follows:

- Treatment Condition: monthly treatment of CSL312 or placebo
- Population: the target patient population defined by eligibility criteria and who were randomized (ITT).
- Variable: time-normalized number of HAE attacks per month during treatment from Day 1 through Day 182.

Intercurrent events: The occurrence of an intercurrent event is irrelevant. All observed values will be used regardless of occurrence of any of the following intercurrent events:

- administration of on-demand medication in addition to prophylactic treatment with CSL312,
- Prohibited concomitant medications due or not due to COVID-19 or COVID-19 vaccination,
- non-compliance to treatment due or not due to COVID-19 or COVID-19 vaccination,
- early study discontinuation due or not due to COVID-19.

- Population-level summary: median time-normalized number of HAE attacks per month during treatment from Day 1 through Day 182 by treatment.

If a subject discontinued the study early after being continuously the first 30 days in the treatment period, the observation is terminated by the Early Termination Visit. It is assumed that the attack rate for subjects, who discontinued the study after the 30th study day and before the end of the 6th month, is comparable to the attack rate from subjects who have the entire 6 months treatment period observed. This assumption is based on CSL312_2001 data which showed that the CSL312 treatment effect was maintained over time. Therefore, the primary endpoint will be considered measurable and not missing, ie, the time-normalized number of HAE attacks will be calculated based on the HAE attacks reported until the Early Termination Visit.

In case a subject discontinues study treatment due or not due to COVID-19 but continues participation in the study for more than 30 days beyond the last study drug administration,

the HAE attacks until the last study drug administration plus 30 days will be included in the HAE attack analysis and length of subject treatment in days will be derived as:

[date of last study drug administration – the date of Study Visit Day 1 of the Treatment Period +31].

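### Staff may withdraw subjects from the study for non-compliance or deviations, which cuts short the follow-up that the treatment-policy primary estimand needs

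*Protocol*

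**What the plan says.** **Withdrawal.** Protocol 4.3.2: "Subjects may withdraw from the study at any time at their own request, or at the discretion of the investigator or CSL", with the example reasons "eg, because of an AE, protocol deviation, loss to follow-up, subject noncompliance, study termination". Protocol 13.4, on deviations generally: "Corresponding subjects may be withdrawn from the study at the discretion of the investigator and / or CSL". Both concern leaving the study. For those who only stop the drug, 4.3.2 says "subjects who discontinue investigational product will be encouraged to remain in the study until Day 182". At withdrawal, 4.3.3 asks only that end-of-treatment assessments be attempted. Withdrawn subjects are not replaced (4.3.5).

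**Estimand.** Protocol 10.3.2.1: "The primary estimand in line with the primary interest of the study follows the treatment policy strategy" and "Intercurrent events: The occurrence of an intercurrent event is irrelevant". Treatment non-compliance and early discontinuation are both listed as such events. SAP 10.1.1 adds prohibited concomitant medication and says "All observed values will be used regardless of occurrence of any of the following intercurrent events". On follow-up, Protocol 10.3.2.1 says "Subjects will be followed after failure to administer or to continue CSL312 treatment until their completion of the study", and then defines completion as the Day 182 visit or an early termination visit, whichever comes first.

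**Analysis after exit.** Under SAP 10.1.1, a subject who leaves the study after the first 30 days is scored on the attacks and days up to the early termination visit. SAP 8.1 and 10.1.1 assume that the unobserved months would have looked the same. A subject who stops treatment but stays more than 30 days beyond the last dose is scored only up to 30 days after that dose.

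**The concern.** A treatment-policy estimand asks what happens to everyone randomized, whatever they do about treatment. It therefore needs outcome data after non-compliance. Sections 4.3.2 and 13.4 let staff end outcome collection at that point, and attacks that were never recorded cannot be recovered at analysis.

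If non-compliant CSL312 subjects drift back toward the placebo rate, scoring them only on their time before exit makes the drug look better than the stated estimand would. Placebo subjects have no drug effect to lose, so the bias would run in one direction. Blinding limits deliberate selection of who is withdrawn, but it does not remove this asymmetry.

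**Working it through.** **1. Inputs.** Monthly rates of 0.3125 (CSL312) and 1.3 (placebo), Poisson, 24:16 completers, about 90% power: Protocol 10.1 and SAP 4.5. Half-life about 19 days: Protocol 1.2.3.1. Concentrations for 50, 75 and 90% attack-risk reduction of 1.4, 3.3 and 7.8 µg/mL: Protocol 3.3.2. Neither document gives an expected number of withdrawals for non-compliance or deviation.

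**2. The plan's own figure.** The O'Brien–Castelloe approximation at 24:16 gives 90.7%, and simulation of the asymptotic Wilcoxon test gives 92.1%. The stated power is reproduced. With all 60 retained (36:24) the formula gives 97.7%. Power is not the issue.

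**3. How a CSL312 subject is scored after becoming non-compliant.**

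| Course | Scored on |
|---|---|
| Withdrawn from the study before 30 days | Missing; covered by the missing-value sensitivity analysis (SAP 10.1.2) |
| Withdrawn from the study after 30 days | Days up to exit; counts as fully observed; not covered by that analysis |
| Misses doses or takes prohibited medication, treatment not discontinued, kept in the study | All attacks to Day 182 |
| Discontinues treatment, stays more than 30 days past the last dose | Days up to last dose + 30 |

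The second and third rows can describe the same subject. Staff discretion decides which applies.

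**4. Size for one subject.** Assume an immediate return to 1.3 per month after exit on day d. If withdrawn, the expected score is 0.3125. If followed to Day 182, it is [0.3125 × d + 1.3 × (182 − d)] / 182:

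- d = 45: 1.06
- d = 60: 0.97
- d = 90: 0.81

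In months, for loss of effect after month 2: (2 × 0.3125 + 4 × 1.3) / 6 = 5.825 / 6 = 0.97.

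**5. Slower loss of effect.** A Hill curve through the three protocol concentrations has exponent about 1.28. Assume a start at 7.8 µg/mL and decay with a 19-day half-life. Falling to 1.4 takes 19 × log2(7.8 / 1.4) = 47 days, and the mean rate over the remaining four months is about 0.78. The six-month rate is then (2 × 0.3125 + 4 × 0.78) / 6 = 0.62. If the effect persists fully, it stays at 0.3125 and the gap is nil.

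**6. Size for the arm, for an assumed fraction f.** Reduction in means = 1 − [(1 − f) × 0.3125 + f × r] / 1.3, against 1 − 0.3125 / 1.3 = 76.0% if all such subjects are scored to exit:

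| f (assumed) | r = 0.97 | r = 0.62 |
|---|---|---|
| 5% | 73.4% | 74.8% |
| 10% | 70.9% | 73.6% |
| 15% | 68.4% | 72.4% |

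The gap from 76.0% is 2.5 to 7.6 points with immediate loss and 1.2 to 3.6 points with slow loss.

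**7. Effect on the primary test.** With six-month Poisson counts and about 15% of the active arm at 0.97, simulation moves the average active-arm median only from about 0.30 to 0.33 per month. Power stays at 100% for both 24:16 and 36:24.

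**The case against.** A reader might infer that the protocol contradicts itself by promising follow-up to Day 182 and then allowing withdrawal. The documents do not support that: the follow-up sentence goes on to allow an early termination visit as the end point, and early discontinuation is itself a listed intercurrent event. The withdrawal wording is also permissive, and non-compliance in 4.3.2 is broader than non-compliance with treatment. All of this stands. It shows that the texts can coexist, but it leaves the length of follow-up to the discretion at issue.

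Second, the protocol change alone would not alter the primary result for subjects who discontinue treatment. With a last dose on Day 31, the SAP length is 31 − 1 + 31 = 61 days, so a subject kept to Day 182 is still scored on about two months. This also stands. The change acts directly only on subjects who miss doses, take prohibited medication or otherwise deviate without discontinuing treatment. Even for missed doses, SAP 10.1.1 leaves room for exclusion of data at blinded review.

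Third, immediate return to 1.3 is an extreme assumption, and the reduction in means is not the primary summary, which is a median with a Wilcoxon test. Both points stand and limit what can be claimed.

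The encouragement to stay to Day 182 does not answer the point. It addresses subjects who stop the product and places no limit on withdrawal initiated by staff. Nor is study withdrawal needed to protect the analysis: SAP Table 9 already provides for per-protocol exclusion for low compliance and prohibited medication.

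**Conclusion.** The point holds as a design weakness, not as a contradiction. Events that the estimand declares irrelevant may be used to end attack collection. The unobserved time is then filled by an assumption of comparability. SAP 10.1.1 supports that assumption by saying that the phase 2 effect was maintained over time, which does not by itself show what happens once dosing lapses. The planned missing-value analysis covers only subjects observed for less than 30 days.

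The effect on the trial result cannot be computed from the documents. For one CSL312 subject lost after month 2, the six-month rate that the estimand targets lies between 0.3125 (effect persists) and 0.97 (immediate return to 1.3), with about 0.62 under the slow-loss assumptions above. It is scored at an expected 0.3125 in every case.

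A reader might take 2.5 to 7.6 percentage points as the expected bias. That would need both immediate full loss of effect and an affected fraction of 5 to 15%, and neither is documented. Nor are the 20 additional subjects a dropout forecast: they also serve safety data and adolescent recruitment, and no dropout rate is stated. The consequence is for the effect size in means, which H02 tests as defined in SAP 4.2. The effect on the primary Wilcoxon test and its power is slight. The change is worth making because it is cheap and the data cannot be recovered later.

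**What to change.** - **Protocol 4.3.2 and 13.4:** remove protocol deviation and subject non-compliance as grounds for withdrawal from the study by the investigator or sponsor. State that these subjects stay in eDiary and attack collection to Day 182 unless they withdraw consent, are lost to follow-up, are withdrawn for safety, or the study ends. A closed list is preferable, because the general reference to behavioral or administrative reasons would let the same grounds back in. Decisions about study drug are unchanged.
- **SAP 10.1.1:** reconcile the cut at 30 days after the last dose with the treatment-policy strategy. Otherwise attacks collected after that point from subjects who stopped treatment are recorded and then left out of the primary analysis.

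Cost: a few sentences in each document, a reminder to sites, and a few more contacts with non-compliant subjects.
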